10.2.2. Sample Size Determination - Part B

No repeat dose MR formulation variability data are currently available. Therefore, the maximum CV_b for the PK parameters were observed in the study 200972 following repeat dose of GSK2982772 capsule formulation; CV_b (%) for AUC_(0-τ) and C_{max} for 20mg QD GSK2982772 IR capsule formulation on Day 1 is 36.1 and 27.1 respectively. Therefore, the estimates of equivalent CV_w (%) are 23.2 and 17.6 for C_{max} and AUC_(0-τ) respectively. Based on these estimates of variability and a sample size of 8 completers, it is estimated that the lower and upper bounds of the 90% confidence interval for the means of AUC_(0-τ) and C_{max} will be within approximately 12.1% and 16.7% of the point estimate respectively.

Sample Size Sensitivity – Part B

Using estimates of parameter (this can be any PK parameter AUC, C_{max}) variability, the precision of these estimates calculated as half width of a 90% confidence interval for the mean and expressed as distance from mean to limits for 4, 6, 8 and 10 participants has been calculated (Table 6).

Table 6 Precision Estimate of Mean – Part B

CV _b (%)	Precision of Mean (%)			
	N=4	N=6	N=8	N=10
18.4%	23.6	16.0	12.8	11.0
19.3%	25.1	16.9	13.6	11.6
24.4%	32.6	21.8	17.4	14.9
25.5%	34.2	22.8	18.2	15.6

For example, based upon the estimate of variability ($CV_b\%$) of 19.3 and a sample size of 4, it is estimated that the lower and upper bounds of the 90% confidence interval for the means of the PK parameter (eg, AUC, C_{max}) will be within approximately 25.1% of the point estimate.

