5.2. Number of Participants

In Part A, 16 healthy participants will be enrolled such that at least 12 evaluable participants complete the study. An evaluable participant will have completed the

planned safety and PK assessments up to 32 hours after dosing (or 24 hours after dosing for Period 3; IR regimen [Regimen C]). An evaluable participant must also have received the relevant test and reference formulations for the comparisons of interest e.g. an MR formulation and the IR reference and/or the selected MR formulation in both the fed and fasted states.

In Part B, 10 healthy participants will be enrolled such that at least 6 evaluable participants complete the study. An evaluable participant will have received all 3 days of dosing at 2 or more dose levels and completed the planned PK assessments up to 24 hours after the first dose on Day 3.

In Part C, 16 participants will be enrolled such that at least 12 evaluable participants complete the study. An evaluable participant will have completed the planned safety and PK assessments up to 32 hours after dosing (or 24 hours after dosing for Period 2; IR regimen). An evaluable participant must also have received the relevant test and reference formulations for the comparisons of interest e.g. the MR tablet and the IR reference at 240 mg.

Participants withdrawn due to an IMP-related AE or termination of the study will not be replaced. If participants prematurely discontinue the study for other reasons, additional replacement participants may be recruited at the discretion of the Sponsor in consultation with the investigator.

Up to 8 replacement participants may be enrolled in Part A. The maximum number of participants that may be dosed in Part A is 24.

Up to 5 replacement participants may be enrolled in Part B. The maximum number of participants that may be dosed in Part B is 15.

Up to 8 replacement participants may be enrolled in Part C. The maximum number of participants that may be dosed in Part C is 24.

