10.2. Sample Size Determination

10.2.1. Sample Size Determination - Part A

To date, there are no MR formulation variability data available. The maximum between-subject coefficient of variation (CV_b) for the PK parameters observed in Study 200975 following GSK2982772 capsule formulation were used for precision estimates; CV_b (%) for $AUC_{(0-inf)}$ and C_{max} for 120 mg GSK2982772 IR capsule formulation were 29.0 and 31.5 respectively. Therefore, the estimates of within subject coefficient of variation (CV_w [%]) are 20.3% and 18.8% for $AUC_{(0-inf)}$ and C_{max} , respectively. Based on these estimates of variability and a sample size of 12 completers, it is estimated that the lower and upper bounds of the 90% confidence interval (CI) for the geometric mean ratio (MR/IR) of AUC and C_{max} will be within approximately 15.3% and 14.2% of the point estimate respectively.

Since it is expected that the MR formulation is to reduce the C_{max} by 50% whilst maintaining the AUC, a sample size of 12 ensures that the 90% CI is within the region 0.8-1.25 for AUC and 0.4-0.625 for C_{max} , if the observed geometric ratio is 0.93-1.08 for AUC and 0.47-0.54 for C_{max} .

Sample Size Sensitivity – Part A

Using estimates of parameter (this can be any PK parameter AUC, C_{max}) variability observed in Study 200975, the precision of these estimates calculated as half width of a 90% confidence interval for the mean ratio (MR/IR) and expressed as distance from mean to limits for 10, 12, 14 and 16 participants has been calculated ([Table 5](#)).

Table 5 Precision Estimate of Mean – Part A

CV _w (%)	Precision of Mean (%)			
	N=10	N=12	N=14	N=16
15	12.70	11.30	10.30	9.50
18.8	16.00	14.20	12.90	11.90
20	17.30	15.30	13.90	12.90

For example, based upon the estimate of variability (CV_w%) of 20 and a sample size of 14, it is estimated that the lower and upper bounds of the 90% confidence interval for the means of the PK parameter (eg, AUC, C_{max}) will be within approximately 13.9% of the point estimate.

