10.2.3. Sample Size Determination - Part C

The maximum between-subject coefficient of variation (CV_b) for the PK parameters observed in Part A of Study 205017 were used for precision estimates; CV_b (%) for $AUC_{(0-inf)}$ and C_{max} were 48.7% and 58.5%, respectively. Therefore, the estimates of within-subject coefficient of variation (CV_w [%]) are 30.9% and 36.7% for $AUC_{(0-inf)}$ and C_{max} , respectively. Based on these estimates of variability and a sample size of 12 completers, it is estimated that the lower and upper bounds of the 90% CI for the geometric mean ratio (MR/IR) of AUC and C_{max} will be within approximately 24.3% and 29.2% of the point estimate, respectively.

Since it is expected that the MR tablet formulation is to reduce the C_{max} by 50% whilst maintaining the AUC, a sample size of 12 ensures that the 90% CI is within the region 0.748-1.342 for AUC and 0.364-0.698 for C_{max} , if the observed geometric ratio is 0.93-1.08 for AUC and 0.47-0.54 for C_{max} .

Sample Size Sensitivity – Part C

Using estimates of parameter (this can be any PK parameter AUC, C_{max}) variability observed in Part A of Study 205017, the precision of these estimates calculated as half width of a 90% CI for the mean ratio (MR/IR) and expressed as distance from mean to limits for 10, 12, 14 and 16 participants has been calculated (Table 7).

Table 7 Precision Estimate of Mean – Part C

CV _w (%)	Precision of Mean (%)			
	N=10	N=12	N=14	N=16
30.9	27.5	24.3	22.0	20.3
36.7	33.1	29.2	26.4	24.3

For example, based upon the estimate of variability ($CV_w\%$) of 30.9 and a sample size of 14, it is estimated that the lower and upper bounds of the 90% CI for the means of the PK parameter (eg, AUC, C_{max}) will be within approximately 22.0% of the point estimate.

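### Protocol 10.2.2 bases the Part B precision of a mean on the within-subject CV; the section's own between-subject CVs give half-widths about 1.6 times wider

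*Protocol*

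**What the plan says.** Protocol 10.2.2 takes between-subject CVs (CVb) from an earlier repeat-dose study of the IR capsule. For AUC(0-tau) and Cmax, in that order, the CVb "on Day 1 is 36.1 and 27.1 respectively". It converts these to equivalent within-subject CVs (CVw), which "are 23.2 and 17.6 for" Cmax and AUC(0-tau), with the order of the parameters now turned round. From these and 8 completers it concludes that the 90% limits for the two means "will be within approximately 12.1% and 16.7% of the point estimate respectively".

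The sensitivity paragraph defines precision as the half-width of a 90% interval "for the mean and expressed as distance from mean to limits for 4, 6, 8 and 10 participants". Table 6 then gives values for CVs of 18.4, 19.3, 24.4 and 25.5%. Both the table heading and the worked example under it call these CVb.

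Parts A and C differ in kind. Sections 10.2.1 and 10.2.3 use CVw for the geometric mean ratio of MR to IR, which is a within-subject comparison.

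On numbers, Protocol 5.2 states: "In Part B, 10 healthy participants will be enrolled such that at least 6 evaluable participants complete the study".

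**The concern.** A mean over participants carries the full spread between participants, so its interval needs CVb. Protocol 10.4.1 defines CVb from the standard deviation of the log-transformed data across participants, which is exactly the quantity required. CVw is the right input for a within-subject ratio, but 10.2.2 describes a mean, not a ratio. Using the smaller CV makes Part B look more precise than 8 participants can deliver.

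There is also a visible inconsistency in the labels. In 10.2.2 AUC has the larger CVb (36.1) but the smaller CVw (17.6). Section 10.2.1 shows the same crossing: for AUC and Cmax the CVb values "were 29.0 and 31.5 respectively", while the CVw values "are 20.3% and 18.8% for" AUC and Cmax.

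What is at stake is the stated planning precision for Part B, and any later use of a table headed CVb that does not contain the CVb values reported beside it.

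**Working it through.** **Inputs.** From Protocol 10.2.2: n = 8; 90% interval; CVb 36.1% (AUC) and 27.1% (Cmax); CVw 17.6% (AUC) and 23.2% (Cmax). From 5.2: minimum 6 evaluable, maximum 15 dosed.

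**Formula.** SD = sqrt(ln(1 + CV²)); half-width = exp(t(0.95, n−1) × SD / sqrt(n)) − 1. At n = 8, t = 1.895.

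**1. Reproducing the printed figures (CVw).**
- CVw 17.6%: SD 0.1747, rounded to 0.17; exp(1.895 × 0.17 / sqrt(8)) − 1 = 12.06%. Printed: 12.1%.
- CVw 23.2%: SD 0.2290, rounded to 0.23; exp(1.895 × 0.23 / sqrt(8)) − 1 = 16.66%. Printed: 16.7%.

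With unrounded SDs the results are 12.4% and 16.6%. The two-decimal rounding is not a convenient fit: with SDs of 0.18, 0.19, 0.24 and 0.25 the same formula reproduces all 16 cells of Table 6. Other constructions from CVw do not match: normal quantile 10.7% and 14.2%; distance to the lower limit 11.0% and 14.2%; untransformed CV 11.8% and 15.5%; paired difference 18.0% and 24.2%.

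**2. The same formula with CVb (unrounded SD).**

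| CVb | SD | N=4 | N=6 | N=8 | N=10 |
|---|---|---|---|---|---|
| 27.1% | 0.2662 | 36.8 | 24.5 | 19.5 | 16.7 |
| 36.1% | 0.3500 | 51.0 | 33.4 | 26.4 | 22.5 |

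The smallest n giving 12.1% or better at CVb 27.1% is 17. The smallest giving 16.7% or better at CVb 36.1% is 16. Both exceed the 15 who may be dosed.

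**3. Size of the understatement.** Paired by size: 19.5 / 12.1 = 1.61 and 26.4 / 16.7 = 1.58. Taking the printed labels literally: AUC 26.4 / 12.1 = 2.18 and Cmax 19.5 / 16.7 = 1.17.

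**4. Label check.** Ratio of log-scale variances, ln(1 + CVw²) / ln(1 + CVb²):

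| Part | As labelled (AUC, Cmax) | With pairs exchanged |
|---|---|---|
| A | 0.500, 0.367 | 29.0 with 18.8: 0.430; 31.5 with 20.3: 0.427 |
| B | 0.249, 0.740 | 36.1 with 23.2: 0.428; 27.1 with 17.6: 0.430 |
| C | 0.428, 0.429 | not needed |

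In Part C, where the CVb values "were 48.7% and 58.5%, respectively" and the CVw values are 30.9% and 36.7%, the labels are already consistent. Once the pairs are exchanged, Parts A and B show the same ratio, close to 3/7. So one label order is reversed in each of 10.2.1 and 10.2.2.

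**5. Where the Table 6 rows may come from.** Applying 3/7 to the log variances of the two CVb values gives CVw of 17.56% and 23.22%. Multiplying by 1.05 and 1.10 gives 18.44, 19.32, 24.38 and 25.54; the printed rows are 18.4, 19.3, 24.4 and 25.5. This origin is inferred; neither document states it.

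**6. If a within-subject target was meant.** SAP 8.2.5.2 models Day 3 against Day 1. For a simple paired ratio the half-width is exp(t(0.95, 7) × SDw × sqrt(2/8)) − 1, which gives 18.0% (CVw 17.6%) and 24.2% (CVw 23.2%). The printed figures are too narrow for this target as well.

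**The case against.** **Nothing turns on it.** Protocol 10.1 tests no hypothesis, 3.1 describes Part B as complete, the dose endpoints are summarised descriptively, and the reported means will carry their observed intervals. This stands, and it fixes the severity.

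**The factor of 1.6 assumes that one label set is reversed.** This also stands. As printed, the factors are 2.2 for AUC and 1.2 for Cmax. The reversal rests on a variance ratio that the documents do not state, although the agreement across Parts A, B and C is close.

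**Table 6 is arithmetically right for the CVs it lists.** True: if its rows were genuine CVb values, the formula would be correct, and their origin in CVw is inference. It remains demonstrable that no row covers 27.1% or 36.1%, so the table does not show the precision for either reported CVb.

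**The target is ambiguous.** The deliberate conversion to CVw and the SAP's Day 3 against Day 1 model could point to a within-subject ratio. The planned descriptive intervals for means are 95%, not 90%. The ambiguity is real, but it does not rescue the figures, because step 6 is also wider than what is printed.

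**The earlier study's CVb might be a pure between-subject component.** A single-occasion mean would then also carry within-subject variance. With the inferred 3/7 ratio the SDs rise by sqrt(1 + 3/7) = 1.195, and the n = 8 half-widths become about 23.8% and 32.3%. Protocol 10.4.1 defines CVb as the spread of the log data across participants, which supports 19.5% and 26.4%. If the other reading applied, the understatement would be larger.

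**Conclusion.** The concern holds, as a minor error in a stated planning figure. The printed 12.1% and 16.7% are what CVw gives in a one-sample interval; they are not the precision of the means that 10.2.2 describes. With the section's CVb values the n = 8 half-widths are 19.5% and 26.4%. The understatement is about 1.6 times with labels aligned either way, or 2.2 times (AUC) and 1.2 times (Cmax) on the labels as printed.

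This rests on log-normal data, on CVb being the across-participant CV as defined in Protocol 10.4.1, and on the target being a single mean. It does not depend on where the Table 6 rows came from. The crossed labels in 10.2.1 matter little: exchanging them swaps 15.3% and 14.2%, a shift of about 1 percentage point for each parameter.

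**What to change.** - Restate the 10.2.2 precision from CVb: 19.5% (CVb 27.1%) and 26.4% (CVb 36.1%) at n = 8, and 24.5% and 33.4% at the minimum of 6 evaluable.
- Check the AUC and Cmax labels for CVb and CVw in 10.2.1 and 10.2.2 against the source study data, correct whichever set is reversed, and only then assign these figures to the two parameters.
- Replace the four Table 6 rows with the two rows in step 2 of the working. If the table's two-decimal SD is kept, the 27.1% row becomes 37.4, 24.9, 19.8 and 16.9; the 36.1% row is unchanged.
- If the Day 3 to Day 1 ratio was the intended target, say so and give about 18.0% and 24.2% at n = 8, noting the simple paired assumption.

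The cost is an erratum to one paragraph and one table, plus a look-up in the source data. No participants are added and no analysis changes. The only downside is a less favourable stated precision for Part B.

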10.2.3. Sample Size Determination - Part C

The maximum between-subject coefficient of variation (CV_b) for the PK parameters observed in Part A of Study 205017 were used for precision estimates; CV_b (%) for $AUC_{(0-inf)}$ and C_{max} were 48.7% and 58.5%, respectively. Therefore, the estimates of within-subject coefficient of variation (CV_w [%]) are 30.9% and 36.7% for $AUC_{(0-inf)}$ and C_{max} , respectively. Based on these estimates of variability and a sample size of 12 completers, it is estimated that the lower and upper bounds of the 90% CI for the geometric mean ratio (MR/IR) of AUC and C_{max} will be within approximately 24.3% and 29.2% of the point estimate, respectively.

Since it is expected that the MR tablet formulation is to reduce the C_{max} by 50% whilst maintaining the AUC, a sample size of 12 ensures that the 90% CI is within the region 0.748-1.342 for AUC and 0.364-0.698 for C_{max} , if the observed geometric ratio is 0.93-1.08 for AUC and 0.47-0.54 for C_{max} .

Sample Size Sensitivity – Part C

Using estimates of parameter (this can be any PK parameter AUC, C_{max}) variability observed in Part A of Study 205017, the precision of these estimates calculated as half width of a 90% CI for the mean ratio (MR/IR) and expressed as distance from mean to limits for 10, 12, 14 and 16 participants has been calculated (Table 7).

Table 7 Precision Estimate of Mean – Part C

CV _w (%)	Precision of Mean (%)			
	N=10	N=12	N=14	N=16
30.9	27.5	24.3	22.0	20.3
36.7	33.1	29.2	26.4	24.3

For example, based upon the estimate of variability ($CV_w\%$) of 30.9 and a sample size of 14, it is estimated that the lower and upper bounds of the 90% CI for the means of the PK parameter (eg, AUC, C_{max}) will be within approximately 22.0% of the point estimate.

10.3. Populations for Analyses

For purposes of analysis, the following populations are defined:

Population	Description
All Participants	All participants who receive at least 1 dose of study treatment and will be the population for reporting of safety and study population data. Participants will be analyzed according to the treatment they actually received.
PK	Participants in the 'All Participants Population' for whom a PK sample was obtained and analysed and will be the population for reporting of PK data.

10.4. Statistical Analyses

10.4.1. Pharmacokinetic Analyses

All PK analyses will be performed on the PK Population.

For all parts of the study, plasma GSK2982772 concentration-time data will be analysed by non-compartmental methods.

In Parts A and C, from the plasma concentration-time data for each of the regimens, the following PK parameters will be determined, as data permit:

- maximum observed plasma concentration (C_{max}).
- time to C_{max} (T_{max}).
- the elapsed time from dosing at which GSK2982772 was first quantifiable in a concentration vs time profile (T_{lag}).
- observed concentration at 12 hours and 24 hours post-dose (C_{12h} and C_{24h}).
- area under the plasma concentration vs time curve ($AUC_{(0-t)}$, $AUC_{(0-24)}$, $AUC_{(0-12)}$ and $AUC_{(0-inf)}$).
- the percentage of AUC extrapolated beyond the last measured time point ($AUC\%extrap$).
- terminal half-life ($t_{1/2}$).
- C_{max} to C_{12h} and C_{max} to C_{24h} ratios.
- relative bioavailability ($Frel_{formulation}$) of test formulations vs reference formulation based on $AUC_{(0-24)}$ and $AUC_{(0-inf)}$ (or $AUC_{(0-t)}$ if $AUC_{(0-inf)}$ can't be derived) and C_{max} .
- relative bioavailability ($Frel_{FE}$) of fed vs fasted based on AUC and C_{max} .

In Part B, from the plasma concentration-time data for each of the regimens, the following PK parameters will be determined, for Day 1 and Day 3, as data permit:

- maximum observed plasma concentration (C_{\max}) for QD dosing. If BID dosing, C_{\max} after morning dose and evening dose.
- time to C_{\max} (T_{\max}) for QD dosing. If BID dosing, T_{\max} after morning dose and evening dose.
- observed concentration at 12 hours and 24 hours post-dose (C_{12h} and C_{24h}).
- area under the plasma concentration-time curve ($AUC_{(0-24)}$) for QD dosing. If BID dosing, $AUC_{(0-12)}$ and $AUC_{(12-24)}$.
- C_{\max} to C_{12} and C_{\max} to C_{24} ratios.
- Dose normalised C_{\max} , C_{12h} , C_{24h} , $AUC_{(0-\tau)}$ (for BID dosing), $AUC_{(0-24)}$ and $AUC_{(0-\infty)}$.
- Relative bioavailability (F_{relFE}) of fed (non-high fat meal) vs fasted based on AUC and C_{\max} (dose corrected as appropriate)

Descriptive statistics (n, arithmetic mean, standard deviation [SD], 95% CI, minimum, median and maximum,) will be calculated by treatment for all PK concentrations over time and for the derived PK parameters. In addition, for loge-transformed PK parameter variables geometric mean, 95% CI and $\%CV_b$ ($100 * \sqrt{(\exp(SD^2) - 1)}$) will be provided, where the SD is the standard deviation of log-transformed data.

Endpoint	Statistical Analysis Methods
Primary	
The primary PK endpoints to compare MR formulations with IR formulations will be summarised descriptively. Ratio of $AUC_{(0-inf)}$, $AUC_{(0-24)}$, ($AUC_{(0-t)}$, if $AUC_{(0-inf)}$ cannot be derived), C_{max}, C_{12} and C_{24} for MR formulation to IR formulation will be computed with 90% CI. C_{max} to C_{12h} and C_{max} to C_{24h} ratio for each MR formulation (120 mg or 240 mg) and the corresponding total dose of IR formulation (120 mg or 240 mg) will be computed with 90% CI.

Secondary	
The secondary endpoints for food effect will be summarised descriptively. In addition, log-transformed $AUC_{(0-inf)}$ ($AUC_{(0-t)}$, if $AUC_{(0-inf)}$ cannot be derived), C_{12h}, C_{24h}, and C_{max} will be analysed using a mixed effects model with regimen as a fixed effect and subject within sequence as a random effect. Point estimates and corresponding 90% CI will be computed for the differences for each GSK2982772 MR formulation (120 mg, 240 mg, 360 mg or 480 mg) taken in the fed state (test) vs the same dose in the fasted state (reference) using the residual error from the model (MSE). The point and interval estimates on the log-scale will then be exponentially back transformed to give estimates of the ratios of geometric means and 90% CI.
 
Within-subject coefficients of variation for $AUC_{(0-inf)}$ and C_{max} will be calculated based on the log_e-Normal distribution: $CV_w (\%) = \sqrt{\exp(mse) - 1} \times 100$, where MSE is the residual error from the model.
 
Statistical analysis of the PK endpoint T_{max} of each GSK2982772 MR formulation administered under both fed and fasted conditions will be separately analysed non-parametrically [Hauschke, 1990]. The point estimates for the medians for each treatment, the median difference and 90% CI for the median difference will be calculated for the contrast (test-reference).

Secondary	
Part B, the secondary PK endpoints for the selected MR formulation at target daily doses of 30, 60 and 240 mg will be summarised descriptively.
 
Part C, the secondary PK endpoints MR at target daily doses of 240 mg, 360 mg, 480 mg and high dose selected in Period 6 will be summarised descriptively.
 
For Part B and Part C, plots of dose vs dose normalised $AUC_{(0-24)}$, $AUC_{(0-12)}$ ($AUC_{(12-24)}$ BID dosing), C_{12h}, C_{24h} and C_{max} (after morning and evening doses if BID dosing) will be generated to determine if there are any dose dependent changes in the absorption of GSK2982772 following repeat dose administration of the selected minitab MR formulation.

Exploratory	
Part B, the exploratory endpoints for non-high fat meal food effect will be summarised descriptively and modelled as specified for the secondary food effect endpoints.

The Reporting and Analysis Plan will describe the planned PK analyses in greater detail.

10.4.2. Safety Analyses

All safety analyses will be performed on the All Participants Population.

Endpoint	Statistical Analysis Methods
Secondary	The safety endpoints will be summarised descriptively.

The Reporting and Analysis Plan will describe the planned safety analyses in greater detail.

10.4.3. Interim Analyses

No formal statistical analyses are planned. However, after Periods 1 to 3 of Part A are complete, the PK data will be analysed which will guide Periods 4, 5 and 6. Periods 4, 5 and 6 will be flexible and the dosing regimen will be dependent on the outcome of preceding periods. There will be the option to either optimise the MR release duration and/or to evaluate the impact of food on the selected MR minitab formulation in a capsule. There will also be the option to cancel Periods 5 and 6 if an optimal formulation is determined in Periods 1 or 2.

There will be an interim review following final period of Part A to determine the formulation, doses, dosing frequency (QD or BID) and prandial state for each dosing period of Part B. The data will be sent to the sponsor by Quotient, from which the decision on formulation and prandial state selection or stopping the study will be made by the Quotient study team (i.e., PI, scientific lead and pharmacokineticist) and sponsor study team (as a minimum the sponsor's medical monitor, CPMS and GCSP). The decision will be documented and signed by the PI as per Quotient Sciences current SOP. Evidence of the decision will be retained in the ISF and GSK Trial Master File.

There will be no interim analysis during Part B of the study.

In Part C, there will be an interim review following completion of Periods 1 and 2 to determine the dose to be used in Periods 3 and 4. A further interim analysis after Period 4 will be used to determine if dosing should be before a standard meal (i.e., delayed standard meal) or after high fat meal in Period 5. There will be a final interim review after Period 5 to determine the dose and food status for Period 6.

See Section 5.1.1 for full details on the criteria for interim decisions.

The Reporting and Analysis Plan will describe the planned interim analyses in greater detail.

